# 2.6.8 Handling of missing values/censoring/discontinuations

Where data for a binary response endpoint are are missing, either because the underlying score was not recorded or because the response was set to missing as part of the handling of intercurrent events, the underlying score (IGA, or EASI) will be imputed using multiple impuation methods and the response derived from this imputed score.

The multiple imputation model will include scores from all visits from randomization up to the time point of imputation.

For endpoints that are analyzed as continuous variables (for example EASI score % change from baseline), missing values will not be imputed. In this cases the MMRM analysis approach is used to handle the missing data.

If a baseline value is missing and required to derive an endpoint, the baseline value will be imputed by the mean of the respective treatment group in the respective randomization stratum.

# 2.7 Safety analyses

Safety will be assessed based on the safety set of patients.

# 2.7.1 Adverse events (AEs)

Adverse events will be coded according to the MedDRA dictionary. The actual MedDRA version used for reporting the adverse events will be described in a footnote of the CSR tables.

Only treatment emergent AEs will be presented. Treatment emergent adverse events are those events that

- started after the first dose of study treatment, or
- were present prior to the first dose of study treatment but increased in severity based on preferred term.

AEs observed four weeks or more after last study treatment intake will not be considered as treatment-emergent.

The purpose of the AE summaries are to understand what AEs are reported within different time periods relative to start of treatment. Thus AEs will be summarized for different time periods to cover the core and extension studies. Since AEs reported in a period may also be affected by AEs in any previous periods of treatment, the treatment groups for periods after 16 weeks will separate subjects who received placebo and the lower ZPL389 doses for the first 16 weeks of their treatment from those who had already received 30mg or 50mg ZPL389 for 16 weeks.

Therefore AEs will be summarized across the following time periods

- AEs with onset date during the first 16 weeks of treatment where treatment group is the treatment group in the core study. This summary will be based on the full safety set.
- AEs with onset date after week 16 but before week 32 of study treatment. This summary will be based on the subset of the safety set comprised of patients who have on study treatment data after week 16. Treatment groups for this summary are
  - 1. Placebo and low dose ZPL389 followed by 30mg ZPL389 (for subjects who received placebo 3mg or 10mg ZPL389 in the core study)
  - 2. Placebo and low dose ZPL389 followed by 50mg ZPL389 (for subjects who received placebo 3mg or 10mg ZPL389 in the core study)
  - 3. 30mg ZPL389 (for subjects who received 30mg ZPL389 in the core study)
  - 4. 50mg ZPL389 (for subjects who received 50mg ZPL389 in the core study)
- AEs with onset date after week 32 of study treatment. This summary will be based on the subset of the safety set comprising patients who have on study treatment data after week 32. By week 32 it is expected that the treatment received in the core study will have less direct influence and therefore treatment groups for this summary are
  - 1. 30mg ZPL389
  - 2. 50mg ZPL389

AE summaries will show, for each treatment group, the number and percentage of subjects

- having any AE,
- having an AE in each primary system organ class
- having each individual AE (preferred term).

Summaries will also be presented for AEs by severity and for study treatment related AEs.

If a subject reported more than one adverse event with the same preferred term, the adverse event with the greatest severity will be presented. If a subject reported more than one adverse event within the same primary system organ class, the subject will be counted only once with the greatest severity at the system organ class level, where applicable.

AEs leading to discontinuation of the study drug will be summarized in a similar way.

Serious adverse events will also be summarized.

Separate summaries will be provided for deaths, serious adverse events, and other significant adverse events leading to discontinuation.

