Section 6	Clarification that subjects should be fasted 3 hours before site visits and until the last ECG is performed		
	Visit days for Week 16 and Week 20 visits have been updated to 113 and 141 days respectively. Therefore dosing at site on Week 16 visit has been removed. A clarification has been added on when sample will be collected at Week 16 visit		
	Unplanned ECG has been added in the table of assessment and time of Post dose ECG at Baseline and Week 4 changed from 0.5h to 2 hours postdose		
Section 6.6.1 and Section 8.3	Allowing Patient Reported Outcomes (PROs) to be collected on paper should the electronic device not be working		

Changes to specific sections of the protocol are shown in the track changes version of the protocol using strike through red font for deletions and red underlined for insertions.

IRBs/IECs

A copy of this amended protocol will be sent to the Institutional Review Board (IRBs)/Independent Ethics Committee (IECs) and Health Authorities.

The changes described in this amended protocol require IRB/IEC and Health Authority approval according to local regulations prior to implementation.

The changes herein affect the Informed Consent. Sites are required to update and submit for approval a revised Informed Consent that takes into account the changes described in this protocol amendment

Amendment 1 (30 January 2018)

Rationale

The original protocol is amended to incorporate health authority feedback prior to the start of enrolment as listed in the table below.

Section	Changes made	
Section 4.1	EASI score at Screening visit for inclusion into trial changed from 12 to 16	
Section 4.2 and Section 7.5	Exclusion threshold and notable value for resting QTcF for female changed from ≥460 to ≥470 msec	
Section 5.6 and Section 7.5	Discontinuation criteria for cardiac disorders aligned with CTCAE grade 2 events	
Section 6	Time of Post dose ECG at Baseline and Week 4 changed to 30 mins postdose	

The sponsor has used this opportunity to simplify and update sections regarding sample size and statistical analysis. Other minor corrections were made such as adding the requirement for fasting 1 hour before ECG measurements.

All changes from the original protocol v00 are indicated in red underlined text (insertions) or red strikethrough (deleted text) in the track changes version of this protocol amendment.

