3.3 Rationale for dose/regimen, route of administration and duration of treatment

The doses of ZPL389 selected for this study are 3 mg, 10 mg, 30 mg, and 50 mg o.d. for 112 days.

ZPL389 is rapidly absorbed following oral administration of single and multiple doses. The estimated terminal half-life of 70-100 hours supports daily dosing of ZPL389.

The safety margins with toxicology findings and current clinical data support the use of the proposed doses. In oral toxicity studies, ZPL389 was well tolerated in rats and cynomolgus monkeys of up to 26 and 39 weeks duration, respectively. The no-observed-adverse-effect levels (NOAELs) could be established at 30 mg/kg/d in rats and 20 mg/kg/day in monkeys which result in safety margins of 20 and 60 for rats and monkeys, respectively, compared to human exposures at 50 mg dose o.d.

Interim analysis results from an ongoing phase 1 study (CZPL389A2101) which investigated single doses up to 400 mg ZPL389 and multiple doses of 50 mg/day and 100 mg/day ZPL389 (administered as drug in capsule formulation for 21 days) in 75 healthy subjects, supports the current dose selection.

Although good efficacy was observed for some endpoints in the AD proof of concept (PoC) study at 30 mg o.d., other endpoints did not show a sufficient differentiation from placebo. Given the dose of 50 mg has already been administered in healthy volunteers and the large safety margin of this dose, the maximum proposed dose in this study is 50 mg o.d.

The 30 mg dose is chosen to investigate whether there is sufficiently increased efficacy at 50 mg vs. 30 mg (the dose used in the AD PoC study). Finally, to enable exploration of the dose response curve, ½ log dose reductions of 30 mg are used, providing a mid-dose of 10 mg and a low dose of 3 mg. Overall, a more than 16-fold dose range is explored.

A dosing period of 16 weeks is expected to result in additional efficacy compared to the AD PoC study, as, unlike placebo, the efficacy of ZPL389 had not plateaued by the end of the 8-week dosing period in the PoC study.

Novartis anticipates that the proposed doses, and hence range of plasma exposures obtained from the study, will enable characterization of the dose and concentration response curves for ZPL389 in atopic dermatitis subjects.

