7.1 Adverse events

An adverse event (AE) is any untoward medical occurrence (e.g., any unfavorable and unintended sign, symptom or disease) in a subject or clinical investigation subject *after providing written informed consent* for participation in the study until the end of study visit. Therefore, an AE may or may not be temporally or causally associated with the use of a medicinal (investigational) product.

In addition, all reports of intentional misuse and abuse of the product are also considered an adverse event irrespective if a clinical event has occurred.

Confidential

The occurrence of adverse events must be sought by non-directive questioning of the subject at each visit during the study. Adverse events also may be detected when they are volunteered by the subject during or between visits or through physical examination findings, laboratory test findings, or other assessments.

Abnormal laboratory values or test results constitute adverse events only if they fulfill at least one of the following criteria:

- they induce clinical signs or symptoms,
- they are considered clinically significant,
- they require therapy.

Clinically significant abnormal laboratory values or test results must be identified through a review of values outside of normal ranges/clinically notable ranges, significant changes from baseline or the previous visit, or values which are considered to be non-typical in subject with underlying disease. Investigators have the responsibility for managing the safety of individual subject and identifying adverse events. Alert ranges for laboratory and other test abnormalities are included in Appendix 1.

Adverse events must be recorded in the appropriate CRF capturing AEs under the signs, symptoms or diagnosis associated with them, accompanied by the following information:

• the severity grade

mild: usually transient in nature and generally not interfering with normal activities

moderate: sufficiently discomforting to interfere with normal activities

severe: prevents normal activities

- its relationship to the study treatment
- its duration (start and end dates) or if the event is ongoing an outcome of not recovered/not resolved must be reported.
- whether it constitutes a serious adverse event (SAE See Section 7.2 for definition of SAE) and which seriousness criteria have been met.
- action taken regarding investigational treatment

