7.2.2 SAE reporting

To ensure subject safety, every SAE, regardless of causality, occurring after the subject has provided informed consent and until 30 days after the last study visit must be reported to Novartis safety within 24 hours of learning of its occurrence. Any SAEs experienced after the 30 day period after the last study visit should only be reported to Novartis safety if the investigator suspects a causal relationship to study treatment.

All follow-up information for the SAE including information on complications, progression of the initial SAE and recurrent episodes must be reported as follow-up to the original episode within 24 hours of the investigator receiving the follow-up information. An SAE occurring at a different time interval or otherwise considered completely unrelated to a previously reported one must be reported separately as a new event.

Information about all SAEs is collected and recorded on the Serious Adverse Event Report Form; all applicable sections of the form must be completed in order to provide a clinically thorough report. The investigator must assess the relationship of each SAE to the investigational treatment complete the SAE Report Form in English, and submit the completed form within 24 hours to Novartis. Detailed instructions regarding the submission process and requirements for signature are to be found in the investigator folder provided to each site.

Follow-up information is submitted as instructed in the investigator folder. Each re-occurrence, complication, or progression of the original event must be reported as a follow-up to that event regardless of when it occurs. The follow-up information should describe whether the event has resolved or continues, if and how it was treated, whether the blind was broken or not, and whether the subject continued or withdrew from study participation.

If the SAE is not previously documented in the Investigator's Brochure or Package Insert (new occurrence) and is thought to be related to the study treatment a Drug Safety and Epidemiology Department associate may urgently require further information from the investigator for health authority reporting. Novartis may need to issue an Investigator Notification (IN) to inform all investigators involved in any study with the same study treatment that this SAE has been reported. Suspected Unexpected Serious Adverse Reactions (SUSARs) will be collected and

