9.5.2 Safety variables

All safety endpoints (i.e. adverse events, laboratory data, vital signs, and ECG) will be summarized by treatment for all subjects of the safety set. All data will be included in the analysis regardless of rescue medication use.

Adverse events

Treatment emergent adverse events (events started after the first dose of study treatment or events present prior to the first dose of study treatment but increased in severity based on preferred term; AEs observed four weeks after last study-drug administration will not be considered as treatment-emergent) will be summarized. AEs will be summarized by presenting, for each treatment group, the number and percentage of subjects having any AE, having an AE in each primary system organ class and having each individual AE (preferred term). Summaries will also be presented for AEs by severity and for study treatment related AEs. If a subject reported more than one adverse event with the same preferred term, the adverse event with the greatest severity will be presented. If a subject reported more than one adverse event with the subject will be counted only once with the greatest severity at the system organ class level, where applicable.

Serious adverse events will also be summarized.

Separate summaries will be provided for deaths, serious adverse events, and other significant adverse events leading to discontinuation.

Non-treatment emergent adverse events will be reported separately.
Laboratory data

The summary of laboratory evaluations will be presented for two groups of laboratory tests (hematology and serum chemistry). Descriptive summary statistics for the change from baseline to each study visit will be presented. These descriptive summaries will be presented by test group, laboratory test and treatment group. Change from baseline will only be summarized for subjects with both baseline and post baseline values. Shifts with respect to normal ranges and number and percentage of notable abnormalities will also be summarized. For each parameter, the maximum change from baseline will be analyzed analogously.

Vital signs

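### SAP 2.7.1 drops, without saying so, the separate reporting of non-treatment-emergent adverse events that protocol 9.5.2 promises

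*SAP*

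**What the plan says.** Protocol 9.5.2 defines treatment-emergent AEs and closes the window four weeks after the last dose: "AEs observed four weeks after last study-drug administration will not be considered as treatment-emergent". It then provides for what falls outside: "Non-treatment emergent adverse events will be reported separately".

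SAP 2.7.1 keeps practically the same cut-off: "AEs observed four weeks or more after last study treatment intake will not be considered as treatment-emergent". It opens the subject, however, with "Only treatment emergent AEs will be presented", and it plans no table or listing of non-emergent events. The same section goes on to promise summaries of serious adverse events (SAEs) and deaths without repeating the emergent limit. SAP 2.7.2 lists deaths. SAP 2.7.1.1 adds QTc and liver-event tables for the core study and a listing of SARS-CoV-2 infections, also with no emergent limit stated.

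Collection runs past the emergent window. Under protocol 7.1, AEs are collected from consent "for participation in the study until the end of study visit". Under protocol 7.2.2, SAEs occurring "until 30 days after the last study visit must be reported to Novartis safety". Under protocol 5.6.2, subjects who stop treatment early should stay in the study and keep to the normal visit schedule.

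SAP Section 4 names two changes from the protocol: no adjudication of confounding medication, and no MCP-Mod analysis.

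**The concern.** The protocol paired a four-week limit with a safeguard, so that whatever the limit removed from the main tables would still be shown elsewhere. The SAP keeps the limit and removes the safeguard. A team programming from the SAP would collect, clean and code off-drug events and then show them in no AE output.

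Safety is a secondary objective of the core study and the primary objective of the extension, and the SAP keeps both in the abbreviated report. SAP 2.7.3 also sends abnormal laboratory results that qualify as AEs through AE reporting, so the same filter reaches them. At stake is whether a reader of the report can see what happened after the drug was stopped. This matters most in subjects who stopped early, whose off-drug follow-up is long. Events between consent and first dose that did not later worsen are non-emergent too, and also drop out.

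**Working it through.** **1. The two rules side by side**

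| Item | Protocol 9.5.2 | SAP 2.7.1 |
|---|---|---|
| End of emergent window | four weeks after last dose | four weeks or more after last intake is excluded |
| Word used for timing | *observed* | *observed* in the rule, onset date in the period tables |
| Non-emergent AEs | reported separately | not presented |
| Change declared? | – | no, neither here nor in Section 4 |

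**2. Inputs for the timing**

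- Dosing length: 112 days. Protocol 3.3 gives the doses as ending "30 mg, and 50 mg o.d. for 112 days".
- End-of-treatment visit: Day 113, the day after the last dose (protocol Table 6-1, footnote 1).
- Follow-up visit: Day 141 (protocol Table 6-1; SAP Table 2-1).
- SAE reporting: 30 days beyond the last visit (protocol 7.2.2).

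**3. Reproducing the plan's visit days**

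Visit day = 7 × week + 1. Week 16: 7 × 16 + 1 = 113. Week 20: 7 × 20 + 1 = 141. Both agree with the documents.

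**4. Subject dosed for the full course who does not enter the extension**

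- Last dose: 113 − 1 = Day 112.
- First non-emergent day: 112 + 28 = Day 140.
- Follow-up visit: 141 − 112 = 29 days after last dose, so one day past the cut-off.
- AE collection outside the window: Days 140 to 141, or 141 − 140 + 1 = 2 days.
- End of SAE reporting: 141 + 30 = Day 171. SAE reporting outside the window: 171 − 140 + 1 = 32 days, of which Days 142 to 171 (30 days) fall after the visit.

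The one-day alignment depends on the actual last dose. With a last dose on Day 111, 112 or 113, the first non-emergent day is 139, 140 or 141. With Day 114 it is Day 142, and a visit on Day 141 then falls inside the window.

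**5. Early discontinuers followed to Day 141**

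First non-emergent day = last dose + 28. Days not presented = 141 − (last dose + 28) + 1.

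| Last dose | Non-emergent from | AE days not presented |
|---|---|---|
| Day 84 | Day 112 | 30 |
| Day 56 | Day 84 | 58 |
| Day 28 | Day 56 | 86 |

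With a last dose on Day 28 there are 141 − 28 = 113 off-drug days, and 86 of them (76%) are outside any planned AE presentation.

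**6. Extension**

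SAP Table 2-1 prints 8130 for Week 116. Assuming 7 × 116 + 1 = 813 is meant, and a last dose the day before, the first non-emergent day is 812 + 28 = 840, and the Week 120 visit is Day 841. The pattern is the same.

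**7. How many subjects could be affected**

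SAP 1.1 anticipated 202 to 230 extension subjects from 360, with a core discontinuation rate of 15% to 25%. At those planning figures, 360 − 230 = 130 to 360 − 202 = 158 subjects would not enter the extension. Core discontinuers would number 0.15 × 360 = 54 to 0.25 × 360 = 90. The trial stopped early, so the real numbers are smaller; the SAP does not give them.

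**The case against.** The case on the other side has force on several points.

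- **The cut-off is the protocol's.** Both the four-week limit and the word *observed* stand in protocol 9.5.2. The SAP did not shorten the window. This stands: the defect is the loss of separate reporting, not the choice of window.
- **Events elicited at Week 20 are not all lost.** A reader might infer from *observed* that anything first mentioned on Day 141 is excluded, whatever its onset. The documents do not support that. The SAP defines emergence by when an event started, and its period tables use onset date. An event reported on Day 141 with onset by Day 112 belongs in the table for the first 16 weeks.
- **Late SAEs may be covered.** A reader might infer that SAEs on Days 140 to 171 are certain to disappear. The SAE sentences do not repeat the emergent limit, so the sponsor could read them as covering all SAEs; but they sit in a section that opens with the word *only*. The text is ambiguous. In addition, for the 30 days after the last visit the documents do not say whether such SAEs would enter the report's tables at all; they go to the sponsor's safety group by their own expedited route.
- **Other outputs exist.** Deaths, QTc and liver-event tables and the SARS-CoV-2 listing carry no stated emergent limit. No time window is given for the QTc and liver tables, so they cannot be assumed to cover off-drug findings.
- **The clinical yield may be low.** Five half-lives at the stated 70 to 100 hours are 5 × 70 / 24 = 14.6 to 5 × 100 / 24 = 20.8 days. The drug has largely cleared before the 28-day cut-off, so many late events may be unrelated.
- **The report is abbreviated, and Section 4 is not exhaustive.** The SAP declares other departures only in the text, for example in 2.3.2 and 2.6.2. That is fair, but 2.7.1 declares nothing, and the SAP does not give abbreviation as the reason.

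None of this answers the basic mismatch between the two documents.

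**Conclusion.** The SAP departs from a protocol commitment on safety reporting and neither declares nor justifies it. Followed as written, it gives no planned AE presentation to events starting four weeks or more after the last dose.

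The size depends on the subject. For one who completes 112 days of dosing and does not enter the extension, it is Days 140 to 141, which take in new findings at an on-schedule follow-up visit. For early discontinuers who remain in follow-up it is 30 to 86 days with a last dose between Day 84 and Day 28. For subjects who enter the extension, Day 141 is on treatment and the core gap does not arise. The presentation of SAEs outside the window is unclear, not demonstrably absent.

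These figures assume that emergence is judged by onset, that four weeks means 28 days, and that visits fall on their nominal days; the protocol allows some drift in both dosing and visits. Events starting on Days 113 to 139 are emergent under this reading, so this filter does not remove them.

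The point should be corrected. It does not touch the efficacy analyses or the decision to stop.

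**What to change.** In SAP 2.7.1:

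1. Replace the restriction with the protocol's rule: main tables of treatment-emergent AEs, plus a listing or count by treatment of non-treatment-emergent AEs, separating those before first dose from those after the window.
2. State that summaries or listings of SAEs and deaths include every such event in the database, regardless of emergence.
3. Define emergence by onset date, replacing *observed*, so that the rule matches the period tables.

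If the sponsor prefers to leave these events out, the omission should be declared and justified in SAP Section 4.

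The emergent window need not be extended to the follow-up visit. That would alter a protocol definition, and it becomes unnecessary once the separate listing is restored.

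The cost is a few lines of SAP text and one or two standard outputs from data already collected. The downside is that a few late, probably unrelated events will be shown.

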# Table 1-2Objectives for the extension study A2203E1

Objectives	Endpoints

[figure not shown]
Included in CSR?

Primary objective

Novartis F	or business use only
SAP	

Page 11 CZPL389A2203

Objectives	Endpoints	Included in CSR?
To assess the short-term and long- term safety of 30 mg o.d and 50 mg o.d ZPL389 with concomitant or intermittent use of TCS and/or TCI up to total of 32 weeks and 116 weeks of treatment.	Frequency of AEs at Week 32 (short- term) and Week 116 (long-term).	Yes
Secondary objectives		
To evaluate the efficacy of 30 mg o.d and 50 mg o.d ZPL389 with concomitant or intermittent use of TCS and/or TCI as assessed by IGA response over time.	IGA score over time (absolute and relative frequencies from core study baseline).	Yes
To evaluate the efficacy of 30 mg o.d and 50 mg o.d ZPL389 with concomitant or intermittent use of TCS and/or TCI as assessed by EASI	EASI score over time (absolute and percent change from core study baseline).	Yes

Novartis SAP	For business use only	Page 12 CZPL389A2203
Objectives	Endpoints	Included in CSR?

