# 2.1.1 General definitions

Study treatment is either placebo or 3, 10, 30 or 50mg ZPL389.

Day 1 is defined to be the first day of administration of any study treatment.

All other study days will be labeled relative to Day 1. For event dates on or after Day 1, studyday for a particular event date is calculated as [Date of event] – [Date of first dose]+1, i.e., Day 2, Day 3, etc., will be one day, two days, etc., after Day 1, respectively. For the dates beforeDay 1, study day for an event date is calculated as [Date of event] – [Date of first dose], i.e., Day - 1, Day -2, etc., will be one day, two days, etc., before Day 1, respectively. Duration of an event will be calculated as (Event end date – Event start date + 1).

The descriptor "Day 0" will not be used.

Screening refers to any procedure (e.g., checking inclusion and exclusion criteria) performed prior to the date of first dose of study treatment. Per protocol, subject informed consent must be obtained prior to performing any study related activity. The date of signing informed consent is the start date of screening period.

Baseline is considered to be the last assessment (including those from unscheduled visits) obtained before the first dose of study treatment. All assessments obtained after first dose of study treatment are considered as post-baseline unless otherwise specified.

In general, a baseline value refers to the last measurement made prior to administration of the first dose of study treatment. However, if no pre-treatment value exists, values obtained after first dose of treatment but on that same day of dosing will be considered as the baseline.

The date of last dose will be collected via the CRF. The end of the treatment period will be defined as the last dose date or last visit in treatment period whichever occurs earlier. i.e., for subjects who discontinued or have their last visit earlier than last dose date, the end of study treatment will be the date of the last study visit in the corresponding treatment period.

The core study treatment period is defined to be the time up until the date of the first visit in the extension study whilst the patient is receiving study treatment.

The extension study treatment period is defined to be the time up from the first visit in the extension study until the end of study treatment

The follow-up period is defined to be the time from last dose of study treatment until the end of the study (latest of core and extension for that patient).

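### AE tables are filled by onset date, so an AE that starts on placebo or low dose and worsens after the switch to 30 or 50 mg stays under the core arm if it is kept as one record

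*SAP*

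**What the plan says.** SAP 2.7.1 presents only treatment-emergent AEs. These are events that "started after the first dose of study treatment, or" that "were present prior to the first dose of study treatment but increased in severity based on preferred term". SAP 2.1.1 fixes what the anchor means: "Study treatment is either placebo or 3, 10, 30 or 50mg ZPL389", and "Day 1 is defined to be the first day of administration of any study treatment". The only reference point is therefore the first core dose, which for a placebo subject is a placebo dose.

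The AEs then go into three tables. The first takes "AEs with onset date during the first 16 weeks of treatment where treatment group is the treatment group in the core study". The second takes "AEs with onset date after week 16 but before week 32 of study treatment", with core placebo, 3 mg and 10 mg subjects kept as separate groups according to whether they moved to 30 or 50 mg. The third takes onsets after Week 32, by 30 or 50 mg. On severity, "If a subject reported more than one adverse event with the same preferred term, the adverse event with the greatest severity will be presented".

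SAP 1.1 says that core placebo, 3 mg and 10 mg subjects are re-randomised 1:1 to 30 or 50 mg in the extension, while 30 and 50 mg subjects continue on their dose. SAP Table 1-2 keeps the extension's primary objective in the report: "To assess the short-term and long- term safety of 30 mg o.d and 50 mg o.d ZPL389", measured by AE frequency. SAP 2.2 analyses the Safety Set by the treatment actually taken.

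**The concern.** The SAP accepts that a worsened event can count as a new signal. It applies that idea once, at the first core dose. For a switcher, the move to 30 or 50 mg is the first exposure to that dose, and for a placebo subject the first exposure to active drug. No rule covers an AE that is ongoing at that moment and then gets worse. The emergence definition closely follows the one in Protocol 9.5.2, which was written for a study with no switch.

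At stake is the AE frequency on 30 and 50 mg among switchers, which is part of the extension's primary endpoint. AEs leading to discontinuation are to be summarised in a similar way. So a mild event that begins on placebo, worsens on 50 mg and ends treatment could be tabulated under placebo. That sits badly with analysis by treatment taken.

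**Working it through.** There is no stated figure to reproduce; the check applies the written rules to test events.

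**Periods.** 16 × 7 = 112 and 32 × 7 = 224. The tables therefore cover onsets on Days 1–112, Days 113–224, and after Day 224. The switch is taken as Day 113, the scheduled Week 16 visit (Protocol Table 6-1). This is an assumption, because the extension protocol is not among the documents.

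| Test AE in a placebo subject who switches | Emergent? | Where it is counted |
|---|---|---|
| (a) Starts Day 60, worsens Day 150, one record | Yes, it began after the first dose | First-16-week table, under placebo; in neither later table |
| (b) As (a), but worsening is a new record dated Day 150 | Yes | Weeks 16–32, in the switch group |
| (c) Worsening is a new record dated Day 240 | Yes | After Week 32, under 30 or 50 mg |
| (d) Starts 10 days before Day 1, worsens Day 150, one record | Yes, by the worsening limb | In none of the three periods |
| (e) Starts Day 115, still on placebo because the Week 16 visit is on Day 120 | Yes | Weeks 16–32, in the switch group |

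**What the cases show.** In (a) the event is already treatment-emergent. Allocation by onset date is what keeps it under placebo, so moving the emergence anchor alone would not change its place. Cases (a) and (b) differ only in how the worsening was recorded. Case (d) does not depend on the switch: any single-record AE that predates Day 1 and worsens on treatment, in any arm, has no period. Case (e) is the same weakness in reverse: a calendar boundary stands in for the actual date of the switch.

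**Which recording convention applies?**
- Protocol 7.1 asks for a start and an end date per AE, and has the event followed to resolution with changes in severity assessed at each visit. This leans towards one record.
- Protocol 7.2.2 makes progression of an SAE follow-up to the original report. This also leans towards one record, but concerns SAE reports only.
- The SAP rule for several AEs with the same preferred term allows for separate records.
- No passage settles it.

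**Severity.** If the record in (a) holds only the worst grade, the Day 150 grade appears in the placebo column of the first-16-week table. A core 30 or 50 mg subject who continues, and whose core-onset AE worsens after Week 16, raises that dose's own column in the same way.

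**Size of the affected group.** Planned allocation is 90:45:45:90:90 (SAP 3), so switchers are (90 + 45 + 45)/360 = 50%. The planned extension size is 202 to 230 (SAP 1.1). This gives 202 × 0.5 = 101 to 230 × 0.5 = 115 switchers, or about 50 to 58 per dose, assuming equal roll-over from all arms.

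**Illustration only, on assumed rates.** If 30% of switchers had an AE ongoing at the switch and 10–20% of those worsened, 0.30 × 0.10 = 3% to 0.30 × 0.20 = 6% of switchers would be affected. The documents contain no such rates.

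**The case against.** Tabulating by onset is a coherent and stated choice. SAP 2.7.1 says the tables are meant to show what is reported in each period since the start of treatment. It recognises carry-over and keeps switchers apart for Weeks 16–32. The extension objective runs on a clock that includes the core weeks, and listings show the full treatment sequence. New AEs after the switch, including SAEs and AEs leading to discontinuation, are still tabulated. Both studies stopped early, and SAP 2.3.1 expects extension disposition to differ from what was intended.

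Much of this stands: it limits the size of the problem and shows that switchers were considered. It does not supply a rule for events ongoing at the switch, and it does not find a place for case (d).

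Three stronger readings are tempting, and the documents do not support them.
- A reader might infer that such events are never counted under 30 or 50 mg. Cases (b) and (c) show that they are, if worsening opens a new record.
- A reader might blame the emergence anchor. The event is emergent already; the onset-date rule places it.
- A reader might infer that the doses are made to look safer than placebo. Continuers' later grades can raise the 30 and 50 mg columns by the same route, so the net direction is unknown.

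**Conclusion.** The point holds conditionally. If a rise in severity is kept in the original AE record, SAP 2.7.1 as written counts an AE that begins on placebo, 3 mg or 10 mg and worsens on 30 or 50 mg only under the core arm. The same condition applies to the pre-Day-1 AE that becomes emergent but belongs to no period. If in addition only the worst grade is stored, grades reached in the extension enter the first-16-week table, for all arms.

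The number of events cannot be derived from the documents. The group exposed to the switch problem was planned at about 101 to 115 subjects, and the early stop makes the actual number lower. The effect falls on the extension's safety summaries. The incidence of AEs with onset in the first 16 weeks is unaffected, though their severity breakdown may shift; efficacy is untouched. Because a retained primary safety objective is involved and the remedy is cheap, this should be corrected.

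**What to change.** 1. State whether a rise in severity opens a new AE record.
2. For subjects whose treatment changes at extension entry, count in the extension tables AEs with onset on or after the first extension dose, plus AEs ongoing at that dose whose severity then increases. Allocate the latter by date of worsening.
3. Allocate AEs that predate Day 1 and worsen on treatment by date of worsening too.
4. In the first-16-week table, use the worst severity reached before the first extension dose, for all arms.

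The cost is SAP wording and a second emergence flag. Where the CRF holds a single grade per event, a query or listing is needed to date the worsening, probably for few subjects. The SAP is dated before database lock, so the rule could be set before the final tables are run.
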